1.2.2 BI 754091 (anti-PD-1 mAb)

BI 754091 is a humanised IgG4Pro isotype anti-PD-1 mAb being developed as an i.v. infusion for the treatment of cancer. BI 754091 has highly human frameworks and a low predicted immunogenicity score. The BI 754091 molecule has a molecular weight of approximately 148 kilodaltons. The antibody is composed of 2 heavy chains (446 amino acids each) and 2 light chains (218 amino acids each). The 4 polypeptide chains of the antibody are linked together by disulfide bonds. Each heavy chain contains one consensus sequence for N-linked glycosylation.

BI 754091 shows strong anti-tumour effects in several mice tumour models with some mice showing a CR. Single and repeat dosing studies showed that BI 754091 was well tolerated (as judged by body weight changes and clinical signs) and resulted in significant tumour growth inhibition ($\geq 83\%$) (BI 754091 Investigator's Brochure; [c07895879](#)).

As of March 2019, BI 754091 is under clinical development and the status of clinical trials are as follows:

- The first-in-man trial of BI 754091 (1381-0001) is being conducted in Western countries. The trial consists of a dose escalation part and an expansion part. In the dose escalation part, dose levels ranging from 80 mg to 400 mg were tested and no DLT was reported. 240 mg was selected as the recommended dose for the expansion part and following clinical trials. As of the data cut-off point of 01 November 2018, 50 patients were treated in total (dose escalation cohorts and expansion cohorts) and the objective response rate was 12% (6 patients with partial response).
- There is an ongoing clinical trial of BI 754091 in Asia (1381-0004). This trial consists of several parts including a dose-finding part for BI 754091 monotherapy. BI 754091 as single agent of 240 mg was administered to six Japanese patients, and no DLT was reported.
- BI 754091 is also being tested in combination with other investigational products in several clinical trials.

1.2.3 Combination of BI 891065 and BI 754091

The rationale for combining BI 891065 and anti-PD-1 is the “one-two-punch” combination model. The first punch is given to the tumour cells directly by the SMAC mimetic BI 891065 in combination with cell death triggers released by the immune system or by the tumour cells themselves (e.g., TNF α), while the second punch leading to decisive, tumour knock-out occurs only after concomitant blockade of the co-inhibitory receptor PD-1 that restores T-cell activity. The killing of tumour cells mediated by SMAC-mimetic may lead to immunogenic cell death ([R16-0468](#); [R16-4658](#)), followed by activation of dendritic cells and ultimately increased T-cell infiltration. Thus, the SMAC-mimetic/PD-1 combination may be effective in tumours with low T-cell infiltrate as suggested by an increased efficacy in syngeneic mouse models that respond poorly to anti-PD-1 monotherapy. In these models, complete tumour regression with high response rates (80% to 90%) can be achieved upon combination of BI 891065 and an anti-PD-1 mAb.

The SMAC mimetics induce rapid degradation of cIAP1, which leads, amongst others, to the activation of the alternative NF-Kb pathway within subsets of immune cells, and stimulation of cytokine secretion. Changes in cytokine levels, as contributors to the 'first punch' will be monitored in peripheral blood.

SMAC-mimetics have been shown to have an immunomodulatory function mediating the induction of systemic cytokines (e.g., Interleukin-6, TNF α etc.) and chemokines (e.g., MCP-1) when administered to animals or humans ([R16-0671](#) and Boehringer Ingelheim [BI] in-house data).

To assess the potential of the combination of BI 891065 (SMAC-mimetic) and BI 754091 (anti-PD-1 mAb) to cause cytokine release different from that induced by the administration of BI 891065, a combination study was conducted in cynomolgus monkeys, the animal species used for the non-clinical program of the monoclonal antibody BI 754091. This study did not provide evidence for a clinically relevant change in the cytokine release profile of BI 891065.

Combination of BI 891065 with BI 754091 did not affect the pharmacokinetics (PK) of BI 754091 in cynomolgus monkeys. Under the conditions of this study, BI 891065 at 15 mg/kg/day was well tolerated in the cynomolgus monkey in the presence or absence of BI 754091 dosed at 10 mg/kg.

For a more detailed description of BI 891065 and BI 754091 profiles, please refer to the current Investigator's Brochures ([c14463420](#) and [c07895879](#)).

At a data cut-off date of 29 March 2019, 3 patients have been treated in a single cohort (BI 891065 200 mg + BI 754091 240 mg). No patient has experienced an SAE, death on study, an AE leading to treatment discontinuation or a \geq Grade 3 AE. One patient has experienced non-serious irAEs (hyperthyroidism and pruritus, both grade 1) which were not treated nor did they lead to dose modification of study drugs.

At the same cut-off date (29 March 2019) seven patients (out of 25, 28 %) in the monotherapy portion (Part A) and two patients (out of 3, 66 %) in the combination therapy portion (Part B) of study 1379-0001 had elevated bilirubin based on safety laboratory measurements. The blood bilirubin increases appeared to be dose-dependent. There were no concomitant abnormalities in other parameters like AST, ALT, Alkaline phosphatase and LDH which could not be explained otherwise (e.g. underlying disease). All increased bilirubin values were maximum Grade 2 and did not lead to dose-reduction or discontinuation of study drug. Aetiology and clinical significance are still under investigation.

Of note, after the data cut-off date, a non-serious immune-related adverse reaction of pneumonitis grade 2 was reported which was considered as a DLT as per Clinical Trial Protocol (CTP) in the highest dose combination cohort (BI 891065 400 mg + BI 754091 240 mg). The event started 16 days after first study drug administration and the patient responded well to high-dose steroids.

1.3 RATIONALE FOR PERFORMING THE TRIAL

Most patients with locally advanced or metastatic tumours will succumb to their disease, justifying the substantial need for novel therapeutic strategies to improve the outcome for these patients. Immune checkpoint inhibition has been shown to be a promising therapeutic strategy. Despite encouraging clinical results with immune checkpoint inhibitors, up to 80% of treated patients do not respond to current checkpoint inhibitor monotherapy ([R15-3588](#); [R15-3778](#)).

Preclinical studies generated evidence of a tumour regression effect of the combination of second mitochondrial activator of caspases (SMAC) mimetic BI 891065 and programmed-cell-death-protein-1 (PD-1) antagonists. In particular, the strong combinatorial effect observed in several syngeneic models in combination with anti-PD-1 supports the combination with PD-1 inhibitors. The PD-1 inhibitor BI 754091 will serve as a combination partner for the SMAC-mimetic BI 891065.

Further clinical development of BI 891065 is planned in combination with BI 754091. This requires phase I clinical investigation of BI 891065 monotherapy in Caucasian and Asian patients. In particular, establishment of clinical safety of BI 891065 monotherapy unaffected by a combination treatment is needed. The first-in-human clinical trial of BI 891065 monotherapy and combination of BI 891065 and BI 754091 (trial 1379-0001) is being conducted in Western countries. This trial (trial 1379-0006) is intended to assess the safety, efficacy and PK of BI 891065 monotherapy and combination of BI 891065 and BI 754091 in Asian patients to establish a safe combination dose for the clinical development in Asia.

1.4 BENEFIT - RISK ASSESSMENT

1.4.1 Benefits

This trial is for patients with no therapy options of proven efficacy, or who are not amenable to standard therapies. BI 891065 and BI 754091 inhibit tumour growth and induce tumour regression in pre-clinical models. Based on pre-clinical results, BI 891065 showed single agent anti-tumour activity in several tumour models. Furthermore, the inhibitory effects of the combination of both compounds have been demonstrated in tumour models and may translate into clinical benefit in cancer patients.

1.4.2 Risks

Table [1.4.2: 1](#) displays the anticipated side effects of the study drugs, based on the mechanism of action, observed clinical data from ongoing studies, and published clinical data for drugs targeting SMAC mimetic and PD-1.

Table 1.4.2: 1 Potential risks, their rationale, and mitigation strategy

Potential risks of clinical relevance for this trial	Summary of data, rationale for the risk	Mitigation strategy
Investigational Medicinal Product BI 891065		
Unexpected adverse events and laboratory abnormalities	Due to limited clinical experience of this drug.	Close monitoring, including implementation of safety monitoring committee (SMC).
Cytokine release syndrome (CRS)	Mode of action of the drug may cause CRS because it promotes release of cytokines. (No safety relevant increases of cytokines measured were observed in the first in human trial 1379-0001 (as of 29 March 2019))	To keep patients hospitalised for 3 days after the first administration of BI 891065. Provide recommendation for the management of CRS in the clinical trial protocol. Cytokine levels are measured.
Photosensitivity	SMAC mimetics may sensitize neoplastic as well as non-neoplastic cells to radiation. Preliminary data for BI891065 from a standard phototoxicity assay in 3T3 mouse fibroblasts seem to confirm this hypothesis.	Patients should be instructed to avoid of exposure to direct sunlight (including sunlamps), to use a sunblock and to wear clothing and sunglasses that protect against sun exposure during treatment and for 4 weeks after the last administration of BI 891065.
Drug-induced liver injury (DILI)	Rare but can be a potentially severe event, thus under constant surveillance by sponsors and regulators for all drugs in development.	Timely detection, evaluation, and follow-up of laboratory alterations in selected liver laboratory parameters to ensure patients' safety.

Table 1.4.2: 1 Potential risks, their rationale, and mitigation strategy (continued)

Potential risks of clinical relevance for this trial	Summary of data, rationale for the risk	Mitigation strategy
Investigational Medicinal Product BI 754091		
Unexpected adverse events and laboratory abnormalities	Due to limited clinical experience of this drug.	Close monitoring, including implementation of safety monitoring committee (SMC).
Immune-related adverse events (irAEs)	irAEs are associated with immune mediated mode of action and can be potentially severe.	Recommendations for the management of irAEs are provided according to international guidelines and product labels of approved PD-1 inhibitors.
Infusion related reactions	As with any mAb, hypersensitivity reactions to study medication administration are possible and they are potentially severe.	Patients with history of severe hypersensitivity reactions to other mAbs are excluded. Recommendations for the management of infusion related reactions are given in section 5.2.6.1.4 .
Drug-induced liver injury (DILI)	Rare but can be a potentially severe event, thus under constant surveillance by sponsors and regulators for all drugs in development.	Timely detection, evaluation, and follow-up of laboratory alterations in selected liver laboratory parameters to ensure patients' safety.
Trial procedures		
Tumour biopsy related AEs (Part B only)	Tumour biopsies are mandatory in Part B. There are known risks associated with biopsies such as pain or bleeding.	The risks are clearly explained in the informed consent document.
Other risks		
NA		

1.4.3 Discussion

Both BI 891065 and BI 754091 are currently tested in early phase clinical trials. In general, the observed safety data from the ongoing clinical trials have been consistent with the anticipated safety profiles of these compounds. No DLTs were reported in preceding trials of BI 891065 and BI 754091 in single agent setting. Pre-clinical results showed that BI 891065 exhibited anti-tumour activity as single agent in several tumour models. Target engagement

Proprietary confidential information © 2021 Boehringer Ingelheim International GmbH or one or more of its affiliated companies

(cIAP degradation in Peripheral Blood Mononuclear Cells) was observed in patients in the dose escalation part of trial 1379-0001. At a dose of 100 mg BI 891065, cIAP1 degradation in blood (mode of action biomarker) of >60% was observed in 2 out of 3 patients. Based on the pre-clinical data, as well as clinical data obtained with BI 754091, the inhibitory effects of PD-1 by BI 754091 may translate into clinical benefit in cancer patients.

A Bayesian Logistic Regression Model (BLRM) design will be used in order to escalate the dose into a range where efficacy or target engagement are expected while still minimizing the risk of undue toxicity.

The starting doses of this trial was selected based on the available data from preceding trials, and are considered to minimise the exposure of patients to sub-therapeutic doses.

Patients will remain under surveillance for 10 hours after the first administration of BI 891065 (i.e., until the blood sampling for PK on day 1 is completed). All trial sites will have emergency resuscitation services and access to intensive care.

Specific attention will be given to immune-mediated adverse events (irAEs), infusion-related reactions, and cytokine release syndrome (CRS). Infusion-related reactions or CRS, amongst others, are defined as adverse events of special interest (AESI) and have to be reported according to the rules defined for serious AE (SAE)-reporting.

A Safety Monitoring Committee (SMC) will be established for the assessment of the trial data to ensure the overall safety of the patients and for making dose escalation decisions and defining the recommended dose (RD) for further development.

In summary, the present trial will implement a number of safety measures to mitigate potential risks. A potential benefit is offered to patients with advanced and/or metastatic malignancies by SMAC-mimetic monotherapy and even more by the combination of a SMAC mimetic with a PD-1 inhibitor. Therefore, treatment with both compounds is considered to have the potential to provide patients with clinical benefit at an acceptable risk.

2. TRIAL OBJECTIVES AND ENDPOINTS

2.1 MAIN OBJECTIVES, PRIMARY AND SECONDARY ENDPOINTS

2.1.1 Main objectives

The primary objective of this trial is:

Part A

- To determine the Maximum tolerated dose (MTD) and/or the recommended dose (RD) of BI 891065 monotherapy for further development in Asian patients with advanced solid tumours

Part B

- To determine the MTD and/or the RD of BI 891065 in combination with a fixed dose of BI 754091 at 240 mg for further development in Asian patients with advanced solid tumours

The definition of MTD and RD are as follows:

- MTD: the highest dose with less than 25% risk of the true DLT rate being equal or above 33% during the MTD evaluation period
- RD: RD is determined by SMC and it may be any dose which fulfil the escalation with overdose control (EWOC) criterion. The SMC may decide to declare a dose as RD without determining the MTD, in consideration of all available data including that from preceding trials.

The MTD will be determined based on the frequency of patients experiencing DLTs during the MTD evaluation period. The MTD evaluation period is defined as first treatment cycle (21 days). At the end of the dose escalation, the BLRM will be rerun using DLTs from all treatment cycles. This result as well as all available data will be used to define the RD.

The secondary objectives are:

Part A

- To document the safety and tolerability, and characterise pharmacokinetics (PK) of BI 891065 as monotherapy in Asian patients with advanced solid tumours

Part B

- To document the safety and tolerability, and characterise PK of the combination therapy of BI 891065 and BI 754091 in Asian patients with advanced solid tumours

2.1.2 Primary endpoint(s)

- Maximum tolerated dose (MTD).

Proprietary confidential information © 2021 Boehringer Ingelheim International GmbH or one or more of its affiliated companies

- Number of patients with Dose Limiting Toxicities (DLTs) in the MTD evaluation period and thereafter.

A BLRM employing the EWOC principle will be used during the escalation phase for selection of doses and for estimation of the MTD. Cohorts of patients will receive escalating doses of BI 891065 single agent or combination of BI 891065 and BI 754091 until the MTD is reached or the highest planned dose has been tested (see section [4.1.3](#)). Each cohort will consist of newly enrolled patients. Estimation of the MTD will be based upon the estimation of the probability of a DLT in the MTD evaluation period in the set of evaluable patients for MTD (section [3.3.4.1](#)).

2.1.3 Secondary endpoint(s)

Part A

- The following pharmacokinetics (PK) parameters of BI 891065 will be calculated in cycle 1:
 - $C_{max,ss}$, AUC_{0-24} and $AUC_{\tau,ss}$ of BI 891065

Part B

- The following PK parameters of BI 891065 and BI 754091 will be calculated in cycle 1:
 - $C_{max,ss}$, AUC_{0-24} and $AUC_{\tau,ss}$ of BI 891065;
 - C_{max} and AUC_{0-504} of BI 754091

Proprietary confidential information © 2021 Boehringer Ingelheim International GmbH or one or more of its affiliated companies

3. DESCRIPTION OF DESIGN AND TRIAL POPULATION

3.1 OVERALL TRIAL DESIGN AND PLAN

This is a Phase I, open-label, non-randomised, multicentre trial of BI 891065 given as single agent (Part A) and in combination with BI 754091 (Part B). The data obtained from the trial will determine the MTD estimate for each Part based on a Bayesian logistic regression model (BLRM) with overdose control ([R13-4803](#)). The BLMR estimates the MTD by updating estimates of the probability of observing a DLT in the MTD evaluation period for each dose level in the trial as patient information becomes available. At any time in the trial, it will not be permitted to escalate to a dose which does not fulfil the EWOC principle (refer to section [7](#)). Dose-escalation will be restricted to a maximum of 100 % from the previous dose.

In Part A, successive cohorts of patients will receive increasing doses of BI 891065. The starting dose of BI 891065 is 100 mg once daily. The dose escalation continues until the MTD is reached, or the safety in the highest planned dose level (400 mg total daily dose of BI 891065) is confirmed. Depending on the occurrence of DLTs or other relevant safety information, SMC may decide to decrease the dose of BI 891065. For any dose-escalation cohort, at least three patients will be enrolled. SMC may decide enrolment of further patients. However, in the case that only two patients are evaluable (i.e. one patient is not evaluable) and neither has experienced a DLT within the MTD evaluation period, then dose-escalation can occur based on these two patients.

A Safety Monitoring Committee decides the size for the next dose escalation cohort. After all patients in a cohort have either experienced a DLT or have been observed for at least the MTD evaluation period without experiencing a DLT, the BLMR will be updated with the newly accumulated data. The overdose risk will then be calculated for each dose, and escalation will be permitted to all doses which fulfil the EWOC criterion and the additional 100 % escalation rule. Based on the model and on other available information, the members of the SMC will reach a joint decision on the next dose level to be investigated.

If DLTs are observed in the first two consecutive patients of a previously untested dose level, subsequent enrolment to that cohort will be stopped. The BLMR will re-run to confirm that the dose level still fulfils the EWOC principle. Based on this information, the SMC will evaluate whether the next patients will be enrolled at the same dose level, or if they are enrolled at a lower dose level.

The SMC may decide to stop the dose escalation phase after the criterion for MTD is fulfilled, or the safety in the highest planned dose level is confirmed in the absence of an MTD. Further patients may be included to confirm this MTD estimate, i.e., to confirm that the EWOC criterion is still fulfilled.

The SMC can declare any dose fulfilling the EWOC criterion as RD, independent of the MTD estimate.

In Part B, successive cohorts of patients will receive escalating daily dose of BI 891065 in

Proprietary confidential information © 2021 Boehringer Ingelheim International GmbH or one or more of its affiliated companies

combination with a fixed dose of BI 754091 at 240 mg once every 3 weeks. The planned starting dose of BI 891065 in Part B is 200 mg, and this cohort will commence after the safety of the same dose level in Part A is confirmed. Other doses may be investigated depending on the safety data obtained from Part A and from the preceding first-in-human trial (1379-0001). SMC will make the decision based on recommendation from BLRM as well as other safety information. BLRM with overdose control will be implemented in Part B incorporating all available information of BI 891065 and BI 754091 to quantify the probability of observing a DLT once patient information becomes available.

The dose escalation will continue until any of the following occurs:

1. the MTD is reached
2. the safety in the highest planned dose level (400 mg) is confirmed
3. the safety at the highest dose tolerated in Part A is confirmed (applicable when this dose is less than 400 mg).

In Part B the dose escalation will follow the approach as described for Part A.

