3.2 DISCUSSION OF TRIAL DESIGN, INCLUDING THE CHOICE OF CONTROL GROUP(S)

This trial is a single-arm trial with multiple dose cohorts and there is no control group. This is a standard design in Phase I trials in Oncology clinical trials where the assessment of MTD, safety and PK are the main objectives.

A Bayesian Logistic Regression Model (BLRM) will be used to guide the dose-finding, in order to escalate the dose into a dose range where efficacy or target engagement may be seen while still minimizing the risk of undue toxicity.

A SMC will be established to ensure the patient safety (for details, see section [8.7](#)). The SMC will monitor the safety data on an ongoing basis, interpret the DLT risk estimate provided by BLRM, and make decisions regarding the dose level to be investigated, the MTD and/or RD, and the necessity of trial plan modifications in case of emerging safety issues.

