4.1.4 Method of assigning patients to treatment groups

There will be no randomisation in this trial, as it is a single-arm open-label trial.

An interactive response technology (IRT) system is used to register participation of patients in the trial. Upon acquisition of informed consent, study sites access the IRT to register patients for screening. After assessment of all inclusion and exclusion criteria, study sites access the IRT to register each eligible patient for treatment, and the IRT system will assign the patient to the cohort which is open for recruitment.

As soon as the planned number of patients in a cohort are registered for treatment, IRT will close the screening until the next cohort is opened for recruitment or until further treatment slots become available in the current cohort. Patients who are already in screening at the time of the closure of the screening and who then meet all eligibility criteria can be registered for treatment. If more patients are eligible than planned number of patients for a cohort, it is exceptionally allowed to register more patients than planned for ethical reasons.

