7. STATISTICAL METHODS AND DETERMINATION OF SAMPLE SIZE

7.1 STATISTICAL DESIGN – MODEL

7.1.1 Part A

The trial will be performed as an open-label trial. The objective of the design is to determine the MTD defined as the highest dose with less than 25% risk of the true DLT rate being above 0.33 (EWOC criterion). The dose-finding of Part A will be guided by a Bayesian 2-parameter logistic regression model with overdose control ([R13-4806](#); [R13-4803](#)).

The model is given as follows:

$$\text{logit}(\pi_d) = \log(\alpha) + \beta * \log(d/d^*),$$

where $\text{logit}(\pi) = \log(\pi/(1-\pi))$.

π_d represents the probability of having a DLT in the MTD evaluation period at dose d , $d^* = 200$ mg is the reference dose, allowing for the interpretation of α as the odds of a DLT at dose d^* , and $\theta = (\log(\alpha), \log(\beta))$ with $\alpha, \beta > 0$ is the parameter vector of the model.

The estimated probability of a DLT at each dose level from the model will be summarized using the following intervals:

Under toxicity: [0.00, 0.16)

Targeted toxicity: [0.16, 0.33)

Over toxicity: [0.33, 1.00]

The BLRM-recommended dose for the next cohort is the level with the highest posterior probability of the DLT rate falling in the target interval [0.16, 0.33) among the doses fulfilling EWOC. Applying the EWOC criterion, it should be unlikely (<25% posterior probability) that the DLT rate at that dose will exceed 0.33. However, the maximum allowable dose increment for the subsequent cohort will be no more than 100 %.

The MTD may be considered reached if one of the following criteria is fulfilled:

- The posterior probability of the true DLT rate in the target interval [0.16 – 0.33] of the MTD is above 0.5, OR
- At least 12 patients have been treated in the dose escalation phase of the trial, of which at least 6 at the MTD.

The SMC may decide stopping the dose escalation phase after the criterion for MTD is fulfilled. Further patients may be included to confirm this MTD estimate. If no DLT is observed at a dose of which the efficacy is considered sufficient, the SMC may decide to include an additional number of patients at this dose level and to declare this dose as the dose recommended for further testing.

The BLRM is set up for a fixed dosing schedule of once daily (q.d.) across dose levels of BI 891065. For the purpose of dose-toxicity modelling, a b.i.d. regimen will be converted in

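### The automatic mid-cohort BLRM check is keyed to the order of DLTs, so in a cohort larger than three a later pair of DLTs prompts no model update, at a dose that may already fail EWOC.

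*Protocol*

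**What the plan says.** Protocol 3.1 sets the within-cohort stop: "If DLTs are observed in the first two consecutive patients of a previously untested dose level, subsequent enrolment to that cohort will be stopped". Its purpose is stated directly afterwards: "The BLMR will re-run to confirm that the dose level still fulfils the EWOC principle". The SMC then decides whether the next patients enter at the same or a lower dose.

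The ordinary model update comes later: "After all patients in a cohort have either experienced a DLT or have been observed for at least the MTD evaluation period" without one. The EWOC limit in 7.1.1 is that "it should be unlikely (<25% posterior probability) that the DLT rate at that dose will exceed 0.33". As a prohibition, 3.1 applies it to moving up: "it will not be permitted to escalate to a dose which does not fulfil the EWOC principle". No sentence applies it to filling a cohort that is already open.

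Cohort size has a minimum but no maximum: "For any dose-escalation cohort, at least three patients will be enrolled. SMC may decide enrolment of further patients". Section 4.1.4 adds that, when more patients in screening prove eligible than were planned, "it is exceptionally allowed to register more patients than planned for ethical reasons".

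Part B (3.1) follows the same approach as Part A.

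**The concern.** The check exists to find out whether an open dose level has stopped meeting EWOC. In the BLRM of 7.1.1 the likelihood depends on how many patients were treated at each dose and how many had a DLT. DLTs in patients 1 and 3, or 2 and 3, therefore give the same posterior as DLTs in patients 1 and 2 once three patients are counted. Only the last pattern triggers the re-run.

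If the cohort has more than three places, the other patterns leave registration open with no model update required until every patient has had a DLT or completed 21 days. Further patients could then start at a dose whose overdose probability is already at or above the trial's own 25% limit.

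**Working it through.** **Inputs.** Part A model (7.1.1): logit(π_d) = log(α) + β·log(d/200). Prior for (log α, log β) from Table 7.1.1: 2: weight 0.9 on means (−3.66, −0.28), SDs (1.20, 0.83), correlation −0.10; weight 0.1 on means (−3, 0), SDs (2, 1), correlation 0. Binomial likelihood. P(OD) is the posterior probability that π_d is at least 0.33, and EWOC requires P(OD) < 0.25. The posterior was computed by numerical grid integration.

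**Reproducing the plan's figures.** The prior probabilities in Table 7.1.1: 3 are matched within 0.002, and all 12 current-dose P(OD) values in Table 10.4.1: 1 within 0.008. Scenario 3 (2/3 at 100 mg) gives 0.308 against 0.316 printed. Scenario 6 (0/3 at 100 mg, then 2/3 at 200 mg) gives 0.192 against 0.193 printed.

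**P(OD) at the current dose after two DLTs there:**

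| Current dose and earlier data | 2/2 | 2/3 | 2/4 |
|---|---|---|---|
| 100 mg, none | 0.486 | 0.308 | 0.200 |
| 200 mg, after 0/3 at 100 mg | 0.296 | 0.192 | 0.128 |
| 200 mg, after 1/3 at 100 mg | 0.608 | 0.459 | 0.343 |
| 200 mg b.i.d. (modelled as 300 mg), after 0/3 at 100 mg and 0/3 at 200 mg | 0.446 | 0.263 | 0.171 |
| 400 mg q.d., after 0/3 at 100 mg and 0/3 at 200 mg | 0.659 | 0.418 | 0.283 |

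The 1/3 at 100 mg in the third row is this trial's own Part A result, as listed in Table 7.1.2: 1. In every row 2/2, the state that triggers the present rule, fails EWOC. Of the states the rule can miss, 2/3 fails in four of the five rows and 2/4 in two.

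**When a place is still open.** Among the orderings of exactly two DLTs in a cohort of n, take away the one the rule catches (patients 1 and 2) and the n − 1 in which the second DLT falls in the last patient:

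- n = 3: 3 − 1 − 2 = 0
- n = 4: 6 − 1 − 3 = 2
- n = 5: 10 − 1 − 4 = 5
- n = 6: 15 − 1 − 5 = 9

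A first cohort of three at a new dose therefore has no gap. In a cohort of four the state at issue is 2/3 with patient 4 still to enter. The 2/4 column matters only from five patients upwards.

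**How often, in a cohort of four.** Assume patients enter one at a time, each outcome known before the next entry, with true DLT rate p.

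- The rule fires with probability p²: 0.33² = 0.109; 0.50² = 0.25.
- The rule is silent with one place open (second DLT in patient 3) with probability 2p²(1 − p): 2 × 0.109 × 0.67 = 0.146; 2 × 0.25 × 0.50 = 0.25.

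In a cohort of five or more, a second DLT in patient 4 also leaves a place open, which adds 3p²(1 − p)². The silent total becomes 0.146 + 0.147 = 0.293 at p = 0.33, and 0.25 + 0.1875 = 0.44 at p = 0.50.

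**The case against.** Four objections have force.

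- **Two DLTs do not always breach EWOC.** A reader might infer that any other ordering leaves enrolment open at a dose that has failed. The protocol's scenario 6 says otherwise: 0.193, with 200 mg recommended again. The breach can also reverse as patients are added: at 400 mg after two clean cohorts, 2/5 gives 0.195. This stands, and it favours re-running the model over treating two DLTs as a verdict.
- **The working cohort size is three.** Section 10.4.1 shows six patients at 400 mg, which might be read as one cohort of six. The same section assumes cohorts of exactly three, so these are two cohorts with an update between them. Twelve patients over three levels also fits cohorts of three. A larger cohort is permitted, not planned.
- **The frequency contrast is easily overstated.** Two or more DLTs occur among four patients with probability 0.69 at p = 0.50, against 0.25 for the rule firing. But the 0.69 includes second DLTs in patient 4, when a cohort of four is already full. The like-for-like figure is 0.25 against 0.25.
- **The SMC can act anyway.** Section 3.2 says "The SMC will monitor the safety data on an ongoing basis, interpret the DLT risk estimate provided by BLRM"; 8.7 has it advise on whether enrolment should go on; 3.1 lets it lower the dose; and 4.1.7 requires DLT reports within 24 hours. The SMC charter is not among the documents and may hold a count trigger. These are real safeguards, but in the protocol none of them obliges anyone to re-run the model. The protocol did not rely on discretion alone for the first two patients.

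**Conclusion.** The concern holds in a limited form. The check's trigger does not match its stated purpose, and the mismatch matters only when a cohort exceeds three through the SMC's choice of size, added patients or over-registration. The dose may then already fail EWOC: P(OD) is 0.418 (2/3) and 0.283 (2/4) at 400 mg after two clean cohorts, and 0.459 and 0.343 at 200 mg after the recorded 1/3 at 100 mg. In other cases it does not: 0.193 for 2/3 at 200 mg after a clean 100 mg cohort, and 0.171 for 2/4 at the 300 mg-equivalent b.i.d. dose after two clean cohorts. In a cohort of four the missed case has probability about 15% at a true rate of 0.33 and 25% at 0.50, against 11% and 25% for the rule firing.

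This rests on the printed Part A prior, on sequential entry, and on counting a patient without a DLT as a completed non-event. If such a patient is still inside the 21 days and is left out, 2/3 becomes 2/2 and P(OD) is higher.

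No weight is placed on Part B. Its printed 0.350 for 2/3 at 200/240 was not reproduced from the printed prior (0.463 without the combination history, about 0.01 with that history fully pooled). The documents do not show that any patient was enrolled through this gap. SAP section 3 reports that Part B was cancelled, and Global Amendment 4 that the primary and secondary endpoint assessments are complete. The value now lies in the design record and in any reuse of the rule.

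**What to change.** Reconcile three pieces of text: the trigger in 3.1, the EWOC purpose stated beside it, and the cohort-size and over-registration provisions in 3.1 and 4.1.4. The aim is that the BLRM re-run depends on the number of DLTs in a cohort that is not yet complete, not on which patients had them. If the SMC charter already contains such a trigger, a cross-reference in 3.1 would be enough. What follows from the re-run, for enrolment and for dose, remains for the sponsor and the SMC to decide.

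The cost is about one sentence in the protocol and an occasional short enrolment hold while the model is re-run. Some of those re-runs will show that EWOC is still met.
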